3.2.3 Exploratory Endpoints

3.2.3.1 *Pharmacokinetic Endpoints*

A population PK analysis approach utilizing sparse plasma sampling will be implemented to assess the pharmacokinetics of intravenous phenobarbital in neonatal seizures. The following phenobarbital pharmacokinetic parameters may be *explored* during the study:

- Observed time to reach maximum drug concentration (T_{max})
- Observed peak drug concentration (C_{max})
- Area under the plasma concentration-time curve (AUC_{0-t}), the percent AUC extrapolated from AUC_{0-t} to infinity AUC_{extrap} and infinity (AUC_{0-inf})
- Apparent terminal elimination rate constant (K_{el})
- Apparent terminal drug elimination half-life (t_{1/2})
- Clearance adjusted by absorption, calculated as dose/AUC_{0-inf} (Cl/F)
- Volume of distribution adjusted by absorption, calculated as Dose/K_{el}•AUC_{0-inf} (V_d/F)

Both free and total phenobarbital will be attempted to be measured in order to assess the variability in protein binding of phenobarbital.

Relationship between potential covariates including co-medication, cooling therapy, renal function, liver function, gestational age and protein binding will be explored. Specific analyses will be detailed in the final pharmacokinetic analysis plan.

3.2.3.2 *Other Exploratory Endpoints*

The endpoints described in [Section 3.2.1](#) and [Section 3.2.2](#) will also be evaluated for different neonatal seizure etiologies. The subpopulations to be evaluated include HIE, stroke and intracerebral hemorrhage.

3.2.3.3 *Justification for Exploratory Endpoints*

Gestational age less than 44 weeks has different seizure etiologies, seizure pathogenesis, and hepatic/renal function, potentially affecting drug efficacy, safety, and/or drug metabolism and elimination. Pharmacokinetic data and analysis are necessary to understand these potential study participant differences ([22](#)). The data collected is also part of the overall safety assessment for the study participants.

3.2.4 Safety Endpoints

The following safety assessments will be performed during the study:

- Type, incidence, and severity of adverse events
- Physical examination (including neurologic exam)
- Vital signs (blood pressure [arterial line], respiration rate, pulse rate, oxygen saturation, and temperature)
- Clinical laboratory tests (hematology, serum chemistry)

3.2.4.1 *Justification for Safety Endpoints*

Safety monitoring is a standard, yet critical component of any clinical trial. The safety assessments in this study are not beyond that of standard safety assessments performed in many clinical studies.

4 Study Design

4.1 Overall Design

This is a multicenter, randomized, double-blinded, active-controlled, parallel study in neonates (defined as ≥ 34 - ≤ 44 gestational weeks). The study will consist of a Screening Period, Double-Blind Treatment Period, Follow-up Period and an Open-Label Extension Period. The study participant population is neonates being admitted to the NICU and requiring continuous video electroencephalography (cvEEG) for seizure detection. One or two parents and/or legal guardians must provide written approval of informed consent, before the neonate can be assessed, monitored and managed in accordance with the study protocol and before any study data can be collected and recorded as study data. The reviewing IRB, based on its standard operating procedures, will determine number of parents/legal guardians who will be required to sign the informed consent.

Upon NICU admission and after parents or legal guardians provide informed consent, neonates will be monitored for electrographic seizures.

Seizures requiring study drug treatment will be defined as cumulative electrographic seizure of at least 30 sec/h (22). Confirmation of electrographic seizures by principal investigator or site designees (recommended to be a pediatric neurologist and/or neurophysiologist) is required. Randomization and study drug administration should start as soon as possible after the 30 sec/h of seizure activity criteria is met ideally within 30 min (maximum two hours) (22). If study drug cannot be administered within two hours of recognition of qualifying seizure burden (≥ 30 sec/h), then study drug should not be administered and the neonate will be discontinued from the study and will be a screen failure.

Following confirmation of seizure criteria, neonates will be randomized in a 1:1 allocation to receive a phenobarbital treatment loading dose of 20mg/kg or 40mg/kg, infused over 30 minutes.

If seizures persist (≥ 30 sec/h of seizure activity) 60 minutes following the start of the initial dose of phenobarbital, neonates receiving an initial dose of 20 mg/kg will receive an additional 20 mg/kg dose. Neonates receiving an initial dose of 40 mg/kg will receive an additional 10 mg/kg dose. Administration of this second loading dose is required to be within 2 hours of recognition of qualifying seizure burden (≥ 30 sec/h). The time period between the first and second dose of study treatment will be determined by the principal investigator or site designee (recommended to be a pediatric neurologist and/or neurophysiologist) review of the cvEEG, but must be at least 30 minutes after infusion is completed and no more than 24 hours after the first dose of study treatment (22).

If the seizure activity continues (≥ 30 sec/h) is still not resolved, study participants may receive a second-line alternative anticonvulsant therapy per institutional protocol. In each treatment arm, the second-line anticonvulsant therapy will be confirmed by the principal investigator or site designee (recommended to be a pediatric neurologist and/or neurophysiologist) and recorded in the study documentation as a concomitant medication.

All phenobarbital treatment doses will be prepared by the unblinded investigational pharmacist. The investigational pharmacist will be unblinded (have access to the treatment arm labels) and will not be involved in the assessment or medical management of the neonate. All other study personnel will be blinded to the first and second phenobarbital dose treatment. Each study treatment arm will be prepared in the same total volume of administration and administered over a **30-minute infusion** in order to maintain the study blind.

Throughout the Treatment Period the neonate will be continuously monitored by cvEEG, vital signs will be recorded, clinical seizure assessment will be recorded, and blood samples will be collected for laboratory safety monitoring and phenobarbital plasma concentrations according to the schedule of activities (Section 1.3). cvEEG monitoring will continue throughout the Treatment

Period and will be discontinued at end of Follow-up Period or upon entering Open Label Extension Period.

A population pharmacokinetic approach will be implemented using sparse sampling collection. Collection of plasma samples for phenobarbital analysis will be obtained after each loading dose and will follow the sampling guidelines in the schedule of activities (Section 1.3). Additional plasma samples will be obtained at the completion of the treatment period or at early study discontinuation. In order to maintain the study blind, the phenobarbital plasma concentrations will not be made available to the study personnel.

Seizure management in the treatment period will be determined by cvEEG monitoring. Recording of all vital signs and collection of laboratory safety monitoring and collection of phenobarbital plasma samples will be dependent on the clinical management and status of the neonate. The principal investigator will be allowed to discontinue the neonate from the study protocol at any time throughout the study protocol and allowed to administer alternative anticonvulsant therapy as medically required or following standard of care guidelines.

The study treatment period for the primary study analysis will end 24 hours after the neonate meets the seizure criteria and receives the initial phenobarbital study dose (i.e. T0-24 hr). Prior to completing the Treatment Period or early study discontinuation, cvEEG assessment, clinical seizure assessment, and vital signs will be recorded, clinical laboratory tests will be performed, and a phenobarbital plasma sample will be collected. The neonate will be monitored for an additional 24 hours (Follow-up Period) after the Treatment Period is completed. During the 24-hour Follow-up Period general seizure activity, administration of additional non-study anticonvulsant medication, and adverse events will be recorded. Neonates requiring ongoing/maintenance intravenous phenobarbital therapy following study treatment completion will enter an Open Label Extension Period (up to 3 days) and will be monitored for safety and additional phenobarbital plasma samples will be obtained while they are on therapy and until hospital discharge. All study related assessments and work related to the study will be compensated by the funding Sponsor.

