1.3 Schedule of Events

Study Procedure	Screening Period	Double-Blind Treatment Period	Follow-Up Period / Early Discontinuation/ End of Study
Study Day(s)	-1-0	0-1	1-2
NICU Admission	X		
Informed Consent	X		
Inclusion/Exclusion Criteria	X		
Delivery History	X		
Medical History	X		
Apgar Score	X		
Physical Examination (includes neurological exam)	X ¹		X ²
Height/Length (include Head Circumference and Abdominal Circumference)	X		
Body Weight	X		
Vital Signs ^{1,3}	X	X	X
Laboratory Safety Tests (Hematology, Chemistry, Coagulation) ^{1,4}	X	X	X
Continuous Video EEG Assessment ⁵	X	X	X
Clinical Seizure Assessment ⁶		X	X
Randomization		X	
Phenobarbital Administration		X	
Phenobarbital Maintenance Administration		X	X
Phenobarbital PK Samples ⁷		X	X
Recording of Additional Anticonvulsant Medication		X	
Prior and Concomitant Medication Review	X	X	X
Adverse Events Evaluation	X	X	X

Protocol
MI-5780

Version: 2.0; 07-Dec-2021

Phenobarbital Sodium Injection

Page 16 of 76

1. All neonates will undergo a baseline physical exam (including a neurologic exam), baseline vital signs (blood pressure, pulse rate, respiration rate, oxygen saturation, and auxiliary or rectal temperature) and baseline laboratory safety tests.
2. Physical examination and neurologic exam to be completed at end of Follow-up Period and/or prior to discharge.
3. Vital signs will be monitored and recorded prior to each (loading dose and second dose) phenobarbital treatment administration and every 15 ± 5 minutes up to 1 hour after the completion of each 30-minute dose infusion. Recording of vital signs will continue to be collected every 4-6 hours post phenobarbital administration through the Treatment Period and until completion of the Follow-up Period or at early study discontinuation. The 4-6 hours is calculated from initial loading dose start of infusion time.
4. Laboratory safety tests will be collected at the completion of the Treatment Period, at end of Follow-up Period and every 24 hours during the Open-Label Extension Period or at time of discharge/early study discontinuation.
5. cvEEG monitoring will be recorded for the study from time of informed consent or start of cvEEG (which ever comes last) and up to 48 hours after first loading dose of phenobarbital.

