1.3.1 Schedule of Events (Open Label Extension Period)

Study Procedure	Open Label Extension Study Day(s)	Open Label Discharge/End of Open Label 2-4
NICU Admission		
Informed Consent		
Inclusion/Exclusion Criteria		
Delivery History		
Medical History		
Apgar Score		
Physical Examination (includes neurological exam)		X ¹
Height/Length (include Head Circumference and Abdominal Circumference)		
Body Weight	X	
Vital Signs	X ²	X ²
Laboratory Safety Tests (Hematology, Chemistry, Coagulation)	X ³	X ³
Continuous Video EEG Assessment ⁴		
Clinical Seizure Assessment	X ⁵	X ⁵
Randomization		
Phenobarbital Administration	X	
Phenobarbital Maintenance Administration	X	
Phenobarbital PK Samples ⁶	X	X
Recording of Additional Anticonvulsant Medication	X	X
Prior and Concomitant Medication Review		X
Adverse Events Evaluation	X	X

1. Physical examination and neurologic exam to be completed prior to discharge.
2. Vital signs will be monitored and recorded prior to each phenobarbital maintenance treatment administration and every 15±5 minutes up to 1 hour after the completion of each 30-minute dose infusion. Recording of vital signs will continue to be collected

Protocol
MI-5780

Version: 2.0; 07-Dec-2021
Phenobarbital Sodium Injection

Confidential

Page 18 of 76

every 4-6 hours hour post phenobarbital administration until the completion of the Open Label Extension Period or at study discharge. The 4-6 hours is calculated from initial loading dose start of infusion time.

3. Laboratory safety tests will continue to be collected every 24 hours during Open-Label Extension Period or at time of discharge/early study discontinuation.
4. cvEEG monitoring will be recorded from time of informed consent or start of cvEEG (which ever comes last) and up to 48 hours and up to 48 hours after first loading dose of phenobarbital. If study participant enters Open Label Extension before end of Follow-up Period, cvEEG recording and monitoring will continue until the 48 hours is complete. cvEEG recording and monitoring after 48 hours is not required per this protocol and will follow site's standard of practice.
5. Clinical seizure assessment will be recorded prior to each phenobarbital maintenance treatment administration and at 30- and 60-minutes after the completion of each 30-minute dose infusion. At the end of each 24-hour Open Label Maintenance Study, whether seizures were observed clinically will be documented in the eCRFs.

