4.1.3 Treatment Period

Treatment Period is from time of first drug administration and up to 24 hours (T0-24 hrs).

The following procedures will be performed during the Treatment Period:

- Review of Inclusion/Exclusion Criteria
- Vital Signs
- Collection and review of Laboratory Tests (Hematology, Chemistry and Coagulation)
- Randomization
- cvEEG recording and monitoring
- Clinical Seizure Assessment
- Initial Phenobarbital Administration
- Additional Phenobarbital Administration
- Phenobarbital Plasma Samples
- Recording of Additional Anticonvulsant Medication
- Concomitant Medication Review
- Adverse Events Evaluation

4.1.4 24 Hour Follow-Up Period /Early Discontinuation/End of Study

Follow-Up Period is from end of Treatment Period and up to 24 hours (T24-48 hrs).

The following procedures will be performed during the Follow-up Period:

- Physical Examination (including neurologic examination)
- Vital Signs
- Collection and review of Laboratory Tests (Hematology, Chemistry and Coagulation)
- cvEEG recording and monitoring
- Clinical Seizure Assessment
- Phenobarbital Plasma Samples
- Recording of Additional non-study Anticonvulsant Medication
- Concomitant Medication Review
- Adverse Events Evaluation

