4.1.5 Open-Label Extension Period

Open-Label Extension Period is from start of first phenobarbital maintenance dose and up to 72 hours. Maintenance cannot be started <24 hours after T0 (e.g., not during Treatment Period). If it is determined that maintenance phenobarbital is no longer needed, study participant will be discontinued from the Open-Label Extension Period and final study assessments will be completed based on schedule of activities (Section 1.3).

The following procedures will be performed during the Open-Label Extension Period:

- Vital Signs
- Physical Examination (including neurologic examination)
- Collection and review of Laboratory Tests (Hematology, Chemistry and Coagulation)
- Clinical Seizure Assessment
- Phenobarbital Administration
- Phenobarbital Plasma Samples every 24 hours
- Recording of Additional Anticonvulsant Medication
- Concomitant Medication Review
- Adverse Events Evaluation

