6.1.2 Dosing and Administration

Following confirmation of seizure criteria, neonates will receive 1 of 2 different phenobarbital treatment dose regimens.

- Phenobarbital 20 mg/kg (first/initial dose) followed by 20 mg/kg (if required)[dose to be prepared from 90 mg/ml vials], or
- Phenobarbital 40 mg/kg (first/initial dose) followed by 10 mg/kg (if required)[dose to be prepared from 90 mg/ml vials]

The initial dose will be administered intravenously over a 30-minute period. If seizures persist and the criteria for a second dose is achieved, a second dose of phenobarbital will be administered.

The time period between the first and second dose of phenobarbital cannot occur within 30 minutes of the end of the first dose. Note: the second loading dose can only be administered while study participant is in the Treatment Period and cannot be administered during the Follow-up Period.

Any additional treatment required must be a second line anticonvulsant and be based on site/institutional protocol/standard operating procedures.

If seizures persist following the second dose of phenobarbital, additional treatment will be based on site/institutional protocol/standard operating procedures or site has the option to administer the phenobarbital maintenance dose. Note, the optional maintenance dose cannot be administered during the Treatment Period. Study participant must enter the Follow-up Period before phenobarbital maintenance dose can be administered.

If study participant qualifies for the optional phenobarbital maintenance dose, the study participant can enter the Open-Label Extension Period.

- Optional Maintenance Dose: 5 mg/kg/day administered intravenously as a single dose over a 30-minute period, no earlier than 24 hours after completion of initial loading dose (dose to be prepared from 55 mg/ml vials)

Treatment administration information should be reported to the study participants treating pediatric physician and entered into their medical records at time of study completion and unblinding of the study participant.

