8.2.8 Continuous Video EEG Monitoring

Continuous video-EEG (cvEEG) monitoring is the gold standard for neonatal seizure detection and quantification and should be used whenever available for seizure detection and differential diagnosis of abnormal appearing, paroxysmal clinical events (25). It is the ideal tool to measure the exact number and duration of seizures, their site(s) of onset and spatial patterns of migration. Multichannel (minimum 8-20 channels) cvEEG monitoring is required for accurate detection of seizures to determine drug response (26).

The following are cvEEG reading **recommendations** during the Screening and Treatment Period for the site neurophysiologist or site designee:

- Review first hour of cvEEG recording as soon as possible.
- If not sure if a pattern is a seizure or study participant does not have 30 seconds/hour seizure burden, review every hour for up to 6 hours followed by every 2 hours for up to 4 hours and then every 4 hours.
- If runs of spike/sharp wave discharges or focal discharges, review every 2 hours for up to 6 hours and then review every 4 hours.
- For any other EEG background/pattern- every 4 hour (if normal not to have to wake up midnight to 6 AM).
- Shortly after reports of suspicious clinical event or 1 hour after start of a therapeutic intervention to evaluate for treatment response (assumes 30-minute infusion).

The following are cvEEG reading recommendations during the Follow-up Period and Open Label Maintenance Period:

- Site is to follow their cvEEG reading standard of practice.

It is also **recommended** that the cvEEG technologist or site designee should remain at the monitor for the first hour of recording to ensure a high-quality recording and to make note of relevant clinical signs. Thereafter, the cvEEG technologist or site designee should re-evaluate the quality of the cvEEG recording frequently and adjust recording leads as required by site's standard of practice. It is also **recommended** that the bedside research staff evaluate the quality of the recording periodically and should contact the technologist or designee if the tracing is suboptimal.

cvEEG recording and monitoring will start at time of informed consent or when study participant is hooked up (whichever is latest) and continue up to 48 hours from start time of first phenobarbital dose. cvEEG recording and monitoring after 48 hours is not required per this protocol and will follow site's standard of practice.

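### Section 4.1 stops cvEEG on entry to the open-label extension, although the rest of the protocol runs it to 48 hours, the window of a secondary endpoint

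*Protocol*

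**What the plan says.** Protocol Section 4.1 (Overall Design) has cvEEG run throughout the Treatment "Period and will be discontinued at end of Follow-up Period or upon entering Open Label Extension Period". This gives two stopping points: the end of Follow-up, or entry to the extension.

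Other current text runs the recording to 48 hours:

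- Section 1.3.1, footnote 4, on early entry to the extension: "If study participant enters Open Label Extension before end of Follow-up Period, cvEEG recording and monitoring will continue until the 48 hours is complete".
- Section 1.3, footnote 5: cvEEG is recorded "up to 48 hours after first loading dose of phenobarbital".
- Section 8.2.8, the dedicated cvEEG section: recording and monitoring "continue up to 48 hours from start time of first phenobarbital dose".
- Section 4.1.4: "Follow-Up Period is from end of Treatment Period and up to 24 hours (T24-48 hrs"), with cvEEG in the list of procedures for that period.

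On when the extension starts, Section 4.1.5 says: "Open-Label Extension Period is from start of first phenobarbital maintenance dose and up to 72 hours". The same section bars maintenance before 24 hours after T0. Section 6.1.2 bars it before 24 hours after completion of the initial loading dose, and allows it once the neonate is in Follow-up.

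On the outcome, Section 3.2.2 lists seizure burden over 48 hours as a secondary endpoint. Section 8.1.1.1 defines total burden as the duration, in minutes, of all seizures on the cvEEG recording.

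**The concern.** A neonate who starts maintenance during Follow-up is covered by two opposite instructions. Under Section 4.1 the recording stops; under footnote 4 of Section 1.3.1 it continues to 48 hours. A site could follow Section 4.1 in good faith, because the procedure list in Section 4.1.5 omits cvEEG and the cvEEG row of the Section 1.3.1 table has no tick, only the footnote marker.

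If the recording stops, later seizures are not on it and cannot be recovered. The case report form is no substitute: Section 8.1.4 asks for the times of all seizures only in the first 2 hours, and after that only for seizures that prompt a drug.

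The SAP does not say what happens to a recording shorter than 48 hours. SAP Section 5.5.3 says only that secondary outcomes are not imputed. A total taken over 24 hours could therefore enter the continuous-outcome model of SAP Section 7.2.2 as though it were a 48-hour value.

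The loss may also be informative. When seizures persist after the second dose, Section 6.1.2 says the "site has the option to administer the phenobarbital maintenance dose". Persistent seizures are not the only route into the extension, however. Section 4.1 says: "Neonates requiring ongoing/maintenance intravenous phenobarbital therapy following study treatment completion will enter an Open Label Extension Period (up to 3 days"). The direction of any bias is therefore not determined.

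**Working it through.** **Inputs**

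- T0 is the start of the first 30-minute (0.5 h) infusion (Protocol 3.2.1).
- Treatment Period: T0 to 24 h (4.1.3). Follow-up Period: 24 to 48 h (4.1.4).
- The extension is entered at the start of the first maintenance dose (4.1.5).
- Earliest maintenance: T0 + 24 h (4.1.5), or 24 h after completion of the loading dose (6.1.2).

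**Step 1: reproduce the 48 hours.** Treatment plus Follow-up = 24 + 24 = 48 h. This agrees with Section 1.3 footnote 5 and Section 8.2.8.

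**Step 2: can the extension start before 48 hours?** Yes. Section 6.1.2 allows maintenance once Follow-up has begun, and the main schedule in Section 1.3 ticks both maintenance and cvEEG in the Follow-up column.

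**Step 3: earliest entry**

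- Section 4.1.5 alone: T0 + 24 h.
- Section 6.1.2, and so both minimums together: 0.5 + 24 = T0 + 24.5 h.

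**Step 4: recording lost under Section 4.1**

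Hours lost = 48 − time of the first maintenance dose; share lost = hours lost / 48.

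| First maintenance dose | Hours lost | Share of 48 h |
|---|---|---|
| T0 + 24 h | 48 − 24 = 24 | 24/48 = 50% |
| T0 + 24.5 h | 48 − 24.5 = 23.5 | 23.5/48 = 49% |
| T0 + 36 h | 48 − 36 = 12 | 12/48 = 25% |
| T0 + 48 h | 0 | 0% |

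**Step 5: the same event under each text**

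| Text | Neonate starts maintenance before 48 h |
|---|---|
| 4.1 | Stop cvEEG |
| 1.3.1 footnote 4 | Continue to 48 h; names this case |
| 1.3 footnote 5; 8.2.8 | Run to 48 h; no exception for the extension |
| 4.1.4 | cvEEG listed for 24 to 48 h; extension not mentioned |

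Only Section 4.1 orders a stop.

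**Step 6: which outcomes are exposed.** Maintenance cannot start before 24 h, so the 24-hour primary endpoint and the 24-hour seizure burden are complete under either reading. The 48-hour burden is the one secondary endpoint measured directly from the hours at risk. Use of alternative anticonvulsants by 48 hours comes from medication records, although fewer detected seizures could affect it indirectly.

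**The case against.** The strongest reply is that the protocol already settles the case. Footnote 4 of Section 1.3.1 is specific and operational, Section 8.2.8 is the dedicated cvEEG section, and Section 4.1 is a design overview that refers monitoring to the schedule. Most sites would probably follow the footnote, and nothing in the documents shows that any site would stop early. The explicit contradiction is with footnote 4. Section 1.3 footnote 5 and Section 8.2.8 support the 48-hour reading without mentioning the extension, and Section 4.1.4 is weaker still.

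It can also be said that the percentages are recording hours per neonate in the worst case, not a share of seizure burden or a trial-level effect. The SAP harm is inferred from silence, since a rule against imputation does not say that unrecorded hours count as zero. Capture of late seizures is also loose for other reasons: Section 8.1.4 limits what goes on the form, and Section 8.2.8 leaves reading during Follow-up to site practice.

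All of this stands as a limit on size. None of it removes the conflict. With up to 30 sites, the stopping time of the instrument behind an endpoint should not depend on which section a site reads first. The archived EEG that Section 8.2.8 requires would allow late seizures to be read afterwards, but only for hours that were recorded.

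**Conclusion.** The concern holds. Section 4.1 contains an operative instruction that contradicts footnote 4 of Section 1.3.1 and does not fit the 48-hour rule in Sections 1.3 and 8.2.8. For an affected neonate the loss is at most 23.5 h (both maintenance minimums respected) to 24 h (Section 4.1.5 alone) of the 48. It falls as maintenance starts later and reaches zero at T0 + 48 h.

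This rests on two conditions: the site follows Section 4.1, and maintenance starts before 48 hours. The documents do not say how many neonates would meet both, so no effect on the treatment comparison can be calculated. The SAP treats secondary outcomes as exploratory (Section 5.6). The point should be fixed, but it does not threaten the primary analysis.

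**What to change.** 1. **Protocol 4.1:** delete the seven-word alternative that ends cvEEG on entry to the extension, leaving the end of Follow-up as the stopping point.
2. **Protocol 1.3.1 table and 4.1.5 list:** show cvEEG recording and monitoring to T0 + 48 h.
3. **SAP:** state that unrecorded hours are not counted as zero burden, that a recording ending before T0 + 48 h is an incomplete 48-hour value, and that the number of such recordings is reported by arm. It should also say, before unblinding, how incomplete values enter the analysis, because excluding them could itself be informative.

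The endpoint can stay as total minutes, and the maintenance start times need no change for this point.

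The cost is seven words, one table cell, one list item and a short SAP addition. The protocol changes need IRB review and approval before they take effect, as the Statement of Compliance requires for any amendment, so they can go into the next one. No procedure is added, since Section 8.2.8 already has cvEEG running to 48 hours.
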